Validation study for the Alertgy non-invasive continuous glucose monitor (ANICGM)

Investigators

M. [name], MPH (Professor of Medicine, endocrinology staff)

[name], MPH (endocrinology fellow)

Study sponsor

Cleveland Clinic Innovations

External personnel

Required to set up the device:

[name] – CEO of Alertgy

[name] - Director of Engineering of Alertgy

Introduction

Diabetes mellitus (DM) affects 30 million people in the United States. To achieve glucose control, most patients are prescribed glucose meters by their physicians. Obtaining glucose levels in this manner necessitates cleaning the fingers, attaching a lancet to a device (or simply using a lancet if a device is not available), pricking the finger with a lancet, placing a drop blood on a strip, and awaiting the readout that results after some chemical reactions. Thereafter, the lancet has to be disposed of in a safe receptacle and the finger has to be blotted to stop the blood from oozing.

The anxiety, pain, and tedious process have led researchers to develop other means of checking glucose levels. There are now continuous glucose monitoring systems (CGMS) that entail inserting a subcutaneous sensor that sends readings through a transmitter. These CGMs may or may not need calibration with a fingerstick glucose reading, and the subcutaneous sensor still has to be changed every 10 -14 days.

The Alertgy non-invasive continuous glucose monitor (ANICGM) is a device that does not entail any subcutaneous insertion of a sensor. It is strapped on to the wrist, and glucose readings are given based on subcutaneous signals (see Description of technology and Description of device below). In 2001, a non-invasive device called Glucowatch Biographer was introduced that also involved subcutaneous signals without needing a subcutaneous insertion. However, for various reasons such as long calibration period and reading inaccuracies, the product did not take off. The ANICGM is a promising device that might overcome the limitations of existing and previous methods of non-invasive glucose measurement.

General aim

This study aims to validate the glucose readings taken from the ANICGM with an approved outpatient glucose meter in patients with type 2 diabetes

Specific aim

- 1) To determine the correlation between glucose readings using the ANICGM an AccuChek Inform II blood glucose meter in patients with type 2 diabetes at baseline and after ingestion of a glucose load throughout a complete glucose excursion

-Rationale: a continuous glucose monitor needs to capture rapid postprandial glucose increases and returns to baseline levels

- 2) To ascertain if the ANICGM calibration is maintained up to 14 days

-Rationale: the ANICGM is being developed for use for multiple days

Note: The results from the ANICGM meter will not be used to guide any aspect of the patient's treatment course.

Description of the technology

The ANICGM uses a weak electromagnetic field generated by its wrist band sensor to look into the body to produce a spectrum that provides a measurement of blood glucose present in the wrist area of the body. The core sensing technology used is dielectric spectroscopy, and has been shown capable of measuring blood glucose, non-invasively, in a laboratory environment (1-3). The system uses proprietary and patented dielectric materials and signal processing to enhance performance in both selectivity and sensitivity for blood glucose measurement.

Much like how a MRI uses a strong magnetic field and its interaction with the body to create a picture of what is inside, the ANICGM uses a safe weak low frequency radiofrequency field to take a picture of a person's chemical spectrum, some of it specific only to blood glucose.

The device sends and receives back signals from the wrist area that are used to generate a dielectric spectrum once every 6 seconds. This spectral data is stored on the device, and then downloaded wirelessly or through USB port to an Alertgy laptop. The POC BG using the Accuchek Inform II will be used to provide calibration values for the ANICGM every 5 minutes in mg/dL, during the calibration process. The POC BG levels will be entered into the Alertgy laptop and a proprietary calibration program will be used to analyze the spectral data collected and will generate a calibration algorithm. The Alertgy support team will provide the ANICGM data to compare to the POC BG data they collected concurrently during the tests.

Description of the device

The present band is about 5 inches long made out of inert plastic material. It is applied to the wrist area and adjusted to a snug fit. All of the materials that make contact with the body are inert. A photo is included below.

(This is the current model. An improved version may be available at the time of the study).

Cleveland Clinic staff will be trained by a written instruction manual in the application and use of the device by Alertgy staff on site. As the device is automated and noninvasive, it is anticipated that the training period will take no longer than two hours maximum.

Preliminary data

[figure not shown]
Data from Alertgy in the graph below shows testing of 8 subjects in their lab showing correlation between the ANICGM (y-axis) and the Abbott Freestyle Neo glucometer (x-axis).

Of the 8 subjects, 3 had type 2 diabetes (2 of whom are on insulin), 2 had prediabetes, and 3 did not have prediabetes or diabetes.

Pearson's correlation was used, $R^2= 0.993$.

Clarke Error Grids

- 8 Subjects
- Single Calibration Method

Inclusion Criteria

Type 2 diabetes on diet or on pharmacologic treatment for diabetes

Hemoglobin A1c (HbA1c) 7.5-10.0%

- below 7.5%, there may not be a demonstrable blood glucose spike
- above 10.0%, subjects are more likely to be symptomatic from hyperglycemia and require treatment during the study

Age 18-75 years old

Exclusion Criteria

Patients taking prandial insulin

Fasting blood glucose by fingerstick <70 mg/dL or >250 mg/dL. Hypoglycemia <70 mg/dL will be treated according to clinic protocol.

Pregnancy

ESRD

Decompensated or acute heart failure

Medications that might cause false readings with glucose meters: acetaminophen, ascorbic acid, dopamine, maltodextrin, mannitol

Conditions that limit the ANICGM such as lesions on the forearms

Other conditions that the investigators deem will affect the conduct of the study

Protocol

There are 3 study visits: Visit 1, Visit 2 (3-14 days after Visit 1) and Visit 3 (5-14 days after Visit 1)

Alertgy personnel will undergo the onboarding process utilized by CCF Innovations called Silkroad/Red Carpet. Personnel undergoing this process complete 8 Comet modules (code of conduct, corporate complaints, HIPPA overview and HIPPA & IS Security Awareness, Emergency Management, Environment of Care, Patient Safety and Energy Savings).

Study Calendar

	Visit 1	Visit 2	Visit 3
	Day 1	3-14 days	5-14 days
Informed Consent	X		
Inclusion/Exclusion	X		
Medical History	X		
Urine Pregnancy Test *	X	X	X
Vitals	X	X	X
Comorbidities	X		
Adverse Events Assessment	X	X	X
Medication Review	X	X	X
Ingest GlucoCrush	X	X	X
Glucose Collection (Fingersticks)	X	X	X

*Women with childbearing potential

For all study visits

The timing of the fingerstick blood glucose checks outlined below are approximate, as there might be occasions where the fingerstick might not be performed at the exact minute specified (for example, patient needing to go to restroom, issues with the Accuchek Inform II glucose meter, etc). Every effort will be made to do the fingerstick at the specified time.

Subject fasts overnight, then proceeds to Cleveland Clinic Main Campus Adult Endocrinology clinic at F20.

Vital signs will be taken.

Women with childbearing potential will have a urine pregnancy test before each study.

Patients will be asked to bring diabetes medications (and related devices) if requiring injections to F20.

If a subject is on basal insulin, the subject will take the basal insulin as close to the usual time as possible.

A baseline fingerstick blood glucose (BG) will be taken using the clinic's Accuchek Inform II glucose meter (time -60 min); this is needed to determine eligibility.

If BG 70-150 mg/dL subject will hold their morning medications or delay taking their diabetes medication until after the procedure (except for basal insulin as above) upon instructions of the investigator.

If BG 151-250 mg/dL, subject will take their diabetes medication at the usual time to prevent symptomatic hyperglycemia.

The ANICGM will be placed on the wrist. Measurements from the ANICGM start immediately. There will be a period of 20 minutes to allow the ANICGM to stabilize to body temperature.

Fingerstick BG will be repeated at time -30 min, -15 min, and 0 min for baseline validation.

At time 0 min, subjects ingest 75 g oral glucose drink (GlucoCrush)

For Visit 1:

Since the ANICGM is using new technology that depends on calculating the slope of the fingerstick glucose change to individualize the calibrations, it is crucial to have frequent fingersticks during Visit 1 for the first hour after the glucose challenge (GlucoCrush).

After the GlucoCrush, fingerstick BG will be done every 5 minutes for 2 hours.

Other continuous glucose devices have done monitoring as frequently as this (see attachment, figure 7, from Choi H, Naylor J, Luzio S, Beutler J, Birchall J, Martin C, Porch A. Design and *In Vitro* Interference Test of Microwave Noninvasive Blood Glucose Monitoring Sensor. IEEE Trans Microw Theory Tech. 2015 Oct 1;63(10 Pt 1):3016-3025)

For Visit 2 and Visit 3:

Fingerstick BG will be taken every 15 minutes for 2 hours after ingestion of GlucoCrush

Other continuous glucose devices have done monitoring as frequently as this (see attachment, figure 8, from Choi H, Naylor J, Luzio S, Beutler J, Birchall J, Martin C, Porch A. Design and *In Vitro* Interference Test of Microwave Noninvasive Blood Glucose Monitoring Sensor. IEEE Trans Microw Theory Tech. 2015 Oct 1;63(10 Pt 1):3016-3025)

For all study visits

Wrist device is removed after each study visit. In-between patients, either same or different day, the device will be cleaned by using Super Sani Cloth wipes, which are the disinfectants we have in the endocrine clinic (active ingredients: dimethyl ethylbenzyl ammonium chloride, isopropyl alcohol)

[figure not shown]

Fig. 7. OGTT I. The sensor response (here the change in bandwidth) is compared with blood glucose levels measured using a “blood-strip” glucometer (Bayer CONTOUR).

[figure not shown]

Fig. 8. OGTT II. Sensor data (change in bandwidth) are measured over a continuous 12-h period involving three food ingestions, and are compared with data from a continuous glucose meter (Medtronic Guardian CGM) and blood-strip glucometer (Bayer CONTOUR), after [27].

Sample Size

It is expected that 10-15 subjects will be enrolled, and that there will be up to 24 paired measures on Visit 1 (every 5 minutes for 2 hours), and 8 paired measures (every 15 minutes for 2 hours) each of the follow-up days. If no errors on the Clarke error grid are observed (as in the preliminary data), the error rate based on the “rule of three”, will be constrained to be no more than 0.5% overall (based on 600 total measures), and no greater than 5% within subject (Jovanovic and

Levy, 1997). Confidence limits for the agreement will depend on the within and between subject variability measures, so formal power calculations on this measure of agreement is not possible.

Statistical analysis

Agreement between glucose measures between systems will be evaluated graphically using Bland-Altman plots, and Clarke error grids. Error rates from the Clarke error grid will be calculated, and 95% confidence limits will be calculated overall, by subject and by day within subject. Similarly, limits of agreement from the Bland-Altman plots will be adjusted to account for repeated measures, as described by Bland and Altman (2007). Analysis will be performed using SAS software (version 9.4; Cary, NC).

Possible adverse effects

The materials for the wrist band are inert and the potential for allergy is low.

Fingersticks can cause pain and discomfort.

The Accuchek Inform II needs a small drop of blood for each fingerstick.

Ingesting GlucoCrush may cause high blood glucose if diabetes is not in optimal control

Should a patient develop acute hyperglycemia with symptoms such as increased thirst/vision changes/headache, patients will be hydrated and assessed for the need for insulin. The F20 clinic has regular insulin and/or fast-acting insulin.

As with any patient who comes to the clinic and develops hypoglycemia, a hypoglycemia protocol is in place for study participants. Signs and symptoms of hypoglycemia include, but are not limited to: weakness, restlessness, nervousness, hunger, and sweating. If a patient develops hypoglycemia during the study follow up period (defined as blood sugar < 70 mg/dL), he/she will be administered 4 oz. (120ml) of juice. If the patient is unable to consume carbohydrate sources by mouth, he/she will receive an intramuscular glucagon injection, which is readily available in the clinic.

Due to the potential risk for hypo- and hyperglycemia during the study period, patients will be strongly encouraged to have assisted transportation to and from the visit. In the event that this is not possible, the investigators will assess the subjects individually which might include recommendations to check fingerstick blood glucose at home prior to the visit, taking glucose tablets, staying after the study for observation and fingerstick blood glucose checks.

Compensation

Each study participant will be compensated \$300 for each completed visit, with a total potential to earn \$900 if all three visits are completed.

Informed Consent

Written informed consent will be obtained from the subjects.

Relationship between Alertgy and Cleveland Clinic

Cleveland Clinic, along with University Hospitals and JumpStart, is a founding partner in the Cleveland location of the Silicon Valley headquartered organization called PlugNPlay platform. The company has a Cleveland location which opened in 2018 and is located at the Global Innovation Center (downtown Cleveland).

Alertgy, was a company that was accepted into the first batch PlugNPlay companies. Numerous meetings were held with Cleveland Clinic, Metro & University Hospitals to show the technology. Subject Matter Experts were convened to learn more about the technology and provide feedback as to how the technology could be enhanced and used in the market.

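### Aim 1 promises a complete glucose excursion, but reference sampling stops at a fixed 2 hours at every visit, so the aim and the sampling window need to be reconciled

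*Combined protocol and SAP*

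**What the plan says.** The Specific aim section sets Aim 1 as the correlation between device and reference meter "at baseline and after ingestion of a glucose load throughout a complete glucose excursion". The rationale below it says that "a continuous glucose monitor needs to capture rapid postprandial glucose increases and returns to baseline levels". Both the rise and the return are therefore part of what the aim sets out to test.

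The Protocol section fixes the reference sampling:

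- Baseline, all visits: "Fingerstick BG will be repeated at time -30 min, -15 min, and 0 min for baseline validation".
- Visit 1: "After the GlucoCrush, fingerstick BG will be done every 5 minutes for 2 hours".
- Visits 2 and 3: "Fingerstick BG will be taken every 15 minutes for 2 hours after ingestion of GlucoCrush".

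The wrist device comes off after each visit. The Sample Size section counts pairs over the same window, up to 24 at Visit 1 and 8 at each later visit. The Statistical analysis section plans Bland-Altman limits and Clarke error rates, the latter overall, by subject and by day within subject. It does not split results by rising and falling glucose.

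**The concern.** The aim is defined by a physiological event, the completion of the excursion, while sampling ends by the clock. Nothing links the two. There is no definition of completion, no rule that depends on glucose having returned, and no reason given why 2 hours is long enough. The cited microwave-sensor study is offered in support of how often samples are taken, not for how long.

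Return within 2 hours cannot be taken for granted here. The Inclusion Criteria set an HbA1c range of 7.5-10.0%, and explain the lower limit by the need for a visible spike. Some subjects also hold or delay their diabetes medication during the test.

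What is at stake is the wording of the conclusion. If glucose is still raised at the last reading, a report that follows Aim 1 as written would claim validation over a complete excursion from data that stop before the end of it.

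**Working it through.** **1. The plan's own count.** Inputs are from the Protocol and Sample Size sections. Scheduled post-load pairs per subject: 120/5 + 120/15 + 120/15 = 24 + 8 + 8 = 40. For 15 subjects, 15 × 40 = 600, and the rule of three gives 3/600 = 0.5%. The stated 600 and 0.5% reproduce at 15 subjects, so the 2-hour window is what the plan intends. None of the 600 pairs is scheduled after 120 minutes.

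**2. Assumptions.** The documents give no rise, peak time, fall rate or duration. The following ranges are assumed for illustration: rise above baseline 80, 130 or 180 mg/dL; peak at 60, 75 or 90 minutes; linear fall of 1 or 2 mg/dL per minute.

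**3. Fall rate needed to be back at baseline by 120 minutes.** Required rate = rise/(120 − peak time).

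- Slowest: 80/(120 − 60) = 1.33 mg/dL per minute.
- Fastest: 180/(120 − 90) = 6.0 mg/dL per minute.

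**4. Glucose above baseline at 120 minutes.** Residual = rise − fall rate × (120 − peak time), set to 0 if negative. Entries are in mg/dL, for falls of 1 and 2 mg/dL per minute.

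| Rise | Peak 60 min | Peak 75 min | Peak 90 min |
|---|---|---|---|
| 80 | 20 and 0 | 35 and 0 | 50 and 20 |
| 130 | 70 and 10 | 85 and 40 | 100 and 70 |
| 180 | 120 and 60 | 135 and 90 | 150 and 120 |

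The range is 0-150 mg/dL.

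**5. How much of the fall is still observed.** Time after the peak is 120 − 60 = 60 minutes down to 120 − 90 = 30 minutes.

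- Visit 1: 60/5 = 12 down to 30/5 = 6 readings, out of 24.
- Visits 2 and 3: 60/15 = 4 down to 30/15 = 2 readings, out of 8 at each visit.

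At least half of the rise is reversed by 120 minutes in 9 of the 18 combinations.

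**6. A different assumed shape.** Take a gamma-shaped curve with share of the rise remaining at time t equal to (t/tp)^k × exp(k(1 − t/tp)), where tp is the peak time and k runs from 2 to 4. At 120 minutes, 6-25% of the rise remains for a peak at 45 minutes, 29-54% for 60 minutes and 83-91% for 90 minutes. For example, tp = 60 and k = 2 give 2² × exp(−2) = 0.54. Only an early peak with a sharp fall comes close to baseline inside the window. This curve is also an assumption.

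**The case against.** The strongest reply is that a fixed 2-hour window conflicts with the aim only if 2 hours is too short in these subjects, and the documents give no figure to show that. This stands. The mismatch in wording is in the text; that the return will be missed is not. The evidence on medication also points both ways: subjects with a fasting value of 151-250 mg/dL take their medication at the usual time, and basal insulin continues.

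Several stronger readings are tempting, and the documents do not support them.

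- A reader might infer that the whole return limb goes unobserved. Step 5 shows otherwise: under the same assumptions, 30-60 minutes of falling glucose are sampled.
- A reader might infer that a device which stays high, or drifts upward with wear, would escape notice. A device stuck at its peak reading would already be in error by the amount the reference had fallen, and those pairs enter the Bland-Altman and Clarke analyses. The fasting readings at -30, -15 and 0 minutes give some view of drift before any load.
- A reader might take the share of table entries at zero (2 of 18) as the chance of return. The grid is arbitrary and its entries carry no weights. It also counts a residual of 10 mg/dL as not returned.
- A reader might infer that sampling must be extended. That would mean longer visits and more fingersticks, and it would lengthen the time for which medication may be held. Offsetting the fingersticks by thinning Visit 1's second hour would remove falling-limb readings and possibly calibration readings, since the Description of the technology specifies 5-minute values during calibration. Nothing in the documents shows that this is needed to make the plan coherent.

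**Conclusion.** The point holds as a mismatch between the aim and the sampling window. Aim 1 and its rationale cover the return to baseline; the schedule ends at 120 minutes regardless. Under the assumed ranges the last reference value lies 0-150 mg/dL above baseline, so the final part of the return may or may not be captured. That range rests wholly on assumed rises, peak times and fall rates, and carries no probability.

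The effect is confined to the complete-excursion and return-to-baseline part of Aim 1. Agreement at baseline, on the rise and up to 120 minutes remains estimable, and the 600 pairs and the 0.5% bound are not affected.

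**What to change.** Reconcile the aim with the window that will be sampled:

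1. Restate Aim 1, and the conclusion to be drawn from it, as agreement at baseline and during the first 2 hours after the glucose load.
2. Before data are collected, state a margin around the 0-minute reference value. For each visit, report whether the last reference value fell within it.
3. Limit any statement about a complete excursion or return to baseline to the visits where it did, and give their number out of all visits. These visits are selected by how fast glucose fell, so the statement should not be carried over to the rest.

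The cost is a narrower stated aim and one extra descriptive line in the report. Sampling times, visit length, fingersticks and the pair counts in the Sample Size section stay as they are.

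### Every planned agreement summary pools rising and falling readings, so none can show whether the device lags the glucose excursion that Aim 1 is about

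*Combined protocol and SAP*

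**What the plan says.** Under Specific aim, Aim 1 compares the two systems "at baseline and after ingestion of a glucose load throughout a complete glucose excursion". The reason given is that "a continuous glucose monitor needs to capture rapid postprandial glucose increases and returns to baseline levels".

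Under Statistical analysis, the methods are stated in one sentence: "Agreement between glucose measures between systems will be evaluated graphically using Bland-Altman plots, and Clarke error grids". For Clarke error rates, "95% confidence limits will be calculated overall, by subject and by day within subject". For Bland-Altman, "limits of agreement from the Bland-Altman plots will be adjusted to account for repeated measures". The section plans nothing by phase of the excursion, rate of change, time since the load or time lag. It omits the correlation named in Aim 1, and it does not say which Clarke zones count as errors.

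Under Sample Size, the one quantified outcome is that of no Clarke errors, which is said to bound the overall error rate at 0.5% on 600 measures.

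**The concern.** The rationale for Aim 1 is about tracking: does the reading follow a fast rise and then the return? A device that trails blood glucose reads low on the way up and high on the way down. Each planned grouping (overall, subject, day within subject) contains both limbs, so the two errors offset each other in the mean difference. A moderate delay may also leave every pair close enough to the reference to avoid the serious Clarke zones.

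At stake is the Aim 1 conclusion. The planned output could show a small mean difference and no serious Clarke errors for a device that misses the rise by 25 to 30 mg/dL. A poor result could not be attributed to lag rather than noise.

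**Working it through.** **The plan's own figure.** 15 subjects x (24 + 8 + 8) pairs = 600, and 3/600 = 0.5%. The overall bound reproduces. It counts errors without regard to when in the excursion a pair was taken.

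**Inputs.** From the documents: post-load fingersticks every 5 minutes (Visit 1) or every 15 minutes (Visits 2 and 3), for 120 minutes. Assumed, because the documents give neither: straight-line glucose curves, a device whose only error is a fixed delay L, and conventional Clarke boundaries (zone A is within 20% of the reference at these levels). Before time 0 glucose is held at its baseline value.

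**Illustration.** Curve 160 mg/dL at 0 min, 280 at 60 min, 200 at 120 min; L = 15 min; 15-minute sampling.

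| Time (min) | 15 | 30 | 45 | 60 | 75 | 90 | 105 | 120 |
|---|---|---|---|---|---|---|---|---|
| Reference | 190 | 220 | 250 | 280 | 260 | 240 | 220 | 200 |
| Delayed device | 160 | 190 | 220 | 250 | 280 | 260 | 240 | 220 |
| Difference | -30 | -30 | -30 | -30 | +20 | +20 | +20 | +20 |

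- Pooled bias: (4 x -30 + 4 x 20)/8 = -5 mg/dL. Rising limb -30, falling limb +20.
- SD: every difference lies 25 from the mean, so SD = sqrt(8 x 625/7) = 26.7.
- Naive limits (not adjusted for repeated measures): -5 ± 1.96 x 26.7 = -57 to +47 mg/dL.
- Largest relative error: 30/190 = 15.8%, so 8 of 8 pairs are in zone A.
- With L = 10 min on the same curve: pooled -3.3, rising -20, falling +13.3, limits -38 to +32, 8 of 8 in zone A.

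**When the pooled bias is small.** With a 15-minute delay and 15-minute sampling, each device reading equals the previous reference reading. The sum of differences therefore telescopes:

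pooled bias = -(glucose at 120 min - glucose at 0 min)/8

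It depends only on how far glucose has returned, not on how badly either limb is tracked.

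| Assumed curve (mg/dL) | Pooled bias | Rising | Falling | Zone A |
|---|---|---|---|---|
| 160, 260 at 60 min, 160 at 120 min | 0/8 = 0.0 | -25.0 | +25.0 | 8 of 8 |
| 160, 280 at 60 min, 200 at 120 min | -40/8 = -5.0 | -30.0 | +20.0 | 8 of 8 |
| 150, 290 at 75 min, 250 at 120 min | -100/8 = -12.5 | -28.0 | +13.3 | 8 of 8 |
| 150, 300 at 90 min, 280 at 120 min | -130/8 = -16.3 | -25.0 | +10.0 | 8 of 8 |

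On the 5-minute Visit 1 schedule the four pooled values are -1.0, -5.8, -13.1 and -16.7.

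**Clarke zones.** No delay of 15 minutes or less gave a zone C, D or E pair on any curve tried. Zone B is different: a steep curve (110, 270 at 50 min, 200 at 120 min) with a 15-minute delay puts 7 of 24 Visit 1 pairs in B. At 20 minutes one assumed curve gave 1 of 24 in zone D; at 30 minutes several gave 1 to 3 of 24.

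**Precision after splitting.** Assume a peak at 60 to 90 minutes. Rising pairs per subject are 12 + 4 + 4 = 20 up to 18 + 6 + 6 = 30; falling pairs are 20 down to 10. With 15 subjects that is 300 to 450 rising and 300 to 150 falling. With no errors, and with the plan's own rule of three, the bounds are 1.0% to 0.67% (rising) and 1.0% to 2.0% (falling).

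**The case against.** The strongest reply is that the planned analysis does react to lag. With no other error, a tracking device has limits of 0 to 0, while the 15-minute delay gives -57 to +47. Anyone reporting the limits as planned would show poor agreement, and a sharp eye might see two bands in the plot. This stands: a lag is not invisible. But a device with no lag, a bias of -5 and random error of SD 26.7 would have the same limits, and the plan sets no acceptable width and does not mark phase on the plot.

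A reader might infer that any lagging device would show near-zero bias and no Clarke errors. The documents do not support that. Entry requires HbA1c 7.5-10.0%, so a return to baseline within 2 hours is not assured, and without it the pooled bias is clearly negative. Zone B pairs arise on steep curves, and because the plan leaves a Clarke error undefined, they may or may not count. Longer delays can reach zone D.

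A reader might also infer that the fingerstick schedule is at fault and that Visit 1 second-hour samples should move to Visit 2. That does not follow either. The protocol ties frequent first-hour sampling at Visit 1 to calibration, and does not say that the second hour is dispensable. Description of the technology refers to 5-minute calibration values. Thinning that hour to every 15 minutes would, with a 60-minute peak, cut falling-limb pairs from 12 + 4 + 4 = 20 to 4 + 4 + 4 = 12 per subject, and would give Visits 2 and 3 different schedules.

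**Conclusion.** The gap holds in a limited form. Aim 1's rationale concerns rise and return, and no planned summary separates them, so none can identify lag or its direction. That part rests on the text alone.

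The size rests on assumed curves and a pure delay. Under them, a lag of about 10 to 15 minutes can appear as a small pooled bias when glucose comes close to baseline within 2 hours, and as zero zone C to E pairs. Among the planned summaries, wider limits would then be the only sign, and their cause could not be read from them. When glucose stays high at 120 minutes, a 15-minute lag gives a pooled bias of about -12 to -17 mg/dL, which understates the error on the rise and has the wrong sign for the fall.

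The data needed to answer the question are collected, so the defect lies in the analysis plan and can be repaired. The change should be made. Confidence is moderate because the curves and lags are assumptions.

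**What to change.** In Statistical analysis:

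1. Report the mean difference, repeated-measures limits of agreement and Clarke zones separately for baseline, rising limb and falling limb. Split at the subject's reference peak at that visit, or by the sign of the reference rate of change; choose one rule in advance.
2. Pair readings by the actual fingerstick time, since the protocol says that the scheduled times are approximate.
3. State which Clarke zones count as errors.
4. Report, as descriptive only, the time shift that best aligns each subject's device trace with the fingersticks at Visits 2 and 3.
5. Base the Aim 1 conclusion on the limb-specific results, keeping the pooled summaries alongside.

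The cost is a few lines of text. Device spectra every 6 seconds and the fingersticks are already planned, so no visit or sample is added. The drawbacks are wider limb-specific intervals, few falling-limb pairs when the peak is late (2 per follow-up visit with a 90-minute peak), some distortion at the split point if the peak is picked from noisy meter values, and an imprecise time shift from about 8 post-load fingersticks per visit.

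### Aim 2: Visit 1 accuracy is at least partly the fit to the calibration readings, so a Visit 1 versus Visits 2-3 comparison mixes fitting optimism with drift

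*Combined protocol and SAP*

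**What the plan says.** The second item under Specific aim is "To ascertain if the ANICGM calibration is maintained up to 14 days". No reference level, margin or drift criterion accompanies it.

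Description of the technology says where the calibration comes from: "The POC BG using the Accuchek Inform II will be used to provide calibration values for the ANICGM every 5 minutes in mg/dL". After these values are entered, "a proprietary calibration program will be used to analyze the spectral data collected and will generate a calibration algorithm".

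Only Visit 1 is sampled at that interval: "After the GlucoCrush, fingerstick BG will be done every 5 minutes for 2 hours". The section for Visit 1 explains that the device needs the slope of the fingerstick change to individualize the calibration, and that "it is crucial to have frequent fingersticks during Visit 1 for the first hour after the glucose challenge". At Visits 2 and 3, "Fingerstick BG will be taken every 15 minutes for 2 hours after ingestion of GlucoCrush".

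Sample Size counts up to 24 Visit 1 readings per subject as paired measures, along with 8 from each follow-up day. Under Statistical analysis, Clarke error rates are reported and "95% confidence limits will be calculated overall, by subject and by day within subject". Bland-Altman limits are to be adjusted for repeated measures. The plan names no held-out Visit 1 readings, no cross-validation and no calibration window.

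**The concern.** Whether calibration is maintained is naturally read as later days against Day 1. In the by-day output, the Day 1 figure describes how well the algorithm reproduces readings that helped to build it. The figures for Visits 2 and 3 describe prediction of new readings. Error is expected to rise between the two even if the device is perfectly stable, and the repeated-measures adjustment deals with correlation, not with this optimism.

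Two explanations of a poor Visit 2 result then cannot be separated: the calibration decayed, or it never predicted well beyond the readings it was fitted to. For a device meant to be worn for several days, these lead to different development decisions. Removing Visit 1 from the accuracy rates cures the optimism there, but leaves no Day 1 level over the glucose excursion with which to tell the two apart.

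**Working it through.** **1. The plan's own count.** With 15 subjects, 15 × (24 + 8 + 8) = 600 pairs, and the rule of three gives 3/600 = 0.5%, as stated under Sample Size. Of these, 15 × 24 = 360 (60%) come from Visit 1. The figure reproduces only if the calibration-visit readings are scored as accuracy data. The 240 pairs from Visits 2-3 alone would give 3/240 = 1.25%.

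**2. Optimism with no drift.** Inputs: n = 24 fitted readings (For Visit 1), or n = 12 if only the first hour is used. The number of fitted terms p is not in the documents, so 2, 5 and 10 are assumed as a range. For a least-squares fit, expected squared error is proportional to 1 − p/n on the fitted readings and about 1 + p/n on new readings under similar conditions. The ratio of error SDs, new to fitted, is √[(1 + p/n)/(1 − p/n)].

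| p | n = 24 | n = 12 |
|---|---|---|
| 2 | √(26/22) = 1.09 | √(14/10) = 1.18 |
| 5 | √(29/19) = 1.24 | √(17/7) = 1.56 |
| 10 | √(34/14) = 1.56 | √(22/2) = 3.32 |

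**3. If only the first hour is fitted.** Half of the 24 Visit 1 pairs are then fitted and half are not. Treating the second hour as ordinary new data, the average Visit 1 squared error is proportional to ½(1 − p/12) + ½(1 + p/12) = 1. The ratio of later visits to all of Visit 1 is √(1 + p/12), which is 1.08, 1.19 and 1.35 for p = 2, 5 and 10. The bias is smaller but keeps its direction.

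**4. Simulation with no drift.** Assumptions: invented glucose-load curves, 5% meter error, two levels of signal noise, and all 24 Visit 1 readings fitted. The last column is the share of pairs more than 20% off, which is only a proxy for Clarke errors.

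| Case | RMSE, Visit 1 to Visits 2-3 (mg/dL) | Pairs more than 20% off |
|---|---|---|
| 2 terms, low noise | 15.0 to 17.2 | 0.3% to 0.8% |
| 10 terms, high noise | 16.0 to 30.7 | 1.1% to 11.1% |

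Part of this gap comes from different glucose ranges at different visits. The ratios in step 2 isolate the optimism.

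**5. Visibility in the planned output.** Treating pairs as independent, the chance that one subject shows no pair more than 20% off is as follows.
- 2 terms, low noise: 0.997^24 = 93% at Visit 1 and 0.992^8 = 94% at a follow-up visit.
- 10 terms, high noise: 0.989^24 = 77% and 0.889^8 = 39%.

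Zero errors in 8 pairs has an exact two-sided 95% upper limit of 1 − 0.025^(1/8) = 37%. Zero in 24 has 14%. Small optimism would be lost in the by-day Clarke display; large optimism would not.

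**The case against.** The strongest reply is that Aim 2 can be read in absolute terms: does the Visit 1 calibration still give acceptable agreement at Visits 2 and 3? Those readings are out of sample, provided they are not used to recalibrate, and need no Day 1 comparator. This stands, and it is why the fix takes its primary result from those visits.

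A reader might go further and infer that the trial will wrongly declare calibration lost. The documents do not support that. They contain no test of Visit 1 against later visits, no margin and no decision rule, so such a misreading is a risk in interpretation, not a planned conclusion. The ratios above concern error SD, which is not the planned Clarke measure, and no section supports any particular number of fitted terms.

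A reader might also infer that Day 1 offers no out-of-sample information at all. That too is more than the text says. The emphasis on the first hour leaves open that the 12 second-hour pairs lie outside the fit. The three fasting sticks up to time 0 are described as serving to validate the baseline. But the plan neither separates the second-hour pairs nor says that the fasting sticks are kept out of calibration, and the latter cover only fasting glucose and are not among the 24 pairs counted.

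Finally, the sentence on Bland-Altman limits can be read as extending the by-day breakdown to them. If so, they carry the same mixture of in-sample and out-of-sample readings.

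**Conclusion.** The point holds as a bias of known direction and unknown size in any comparison of Visit 1 with Visits 2-3. It rests on the Visit 1 fingersticks building the calibration, which the text supports, and on follow-up readings not being used to recalibrate, which Aim 2 implies but the plan does not state. Under a linear fit to 24 points with no drift, the expected error-SD ratio runs from 1.09 to 1.56 for 2 to 10 terms. A calibration with few terms makes this a modest matter; a flexible spectral model makes it a serious one. Aim 2 remains answerable in absolute terms from Visits 2-3. What the plan cannot do as written is separate drift from a calibration that was overfitted on Day 1. The plan should be changed because the remedy uses data already being collected.

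**What to change.** In Statistical analysis:

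1. State which Visit 1 fingersticks enter the calibration (first hour or full two hours, and whether the fasting sticks are included), and freeze each subject's algorithm before Visit 2.
2. Label Visit 1 readings used in the fit as calibration data wherever they are reported.
3. Take the primary Aim 2 result from Clarke and Bland-Altman agreement at Visits 2 and 3 with the frozen algorithm.
4. For the Day 1 reference level, re-run the calibration program leaving out one contiguous 20-30 minute block of Visit 1 at a time, and score only the left-out block. Blocks are needed because neighbouring 5-minute readings are correlated, so leaving out alternate points would still be optimistic. The final algorithm keeps its full set of fitted readings.
5. Treat any change from Visit 2 to Visit 3 against days since Visit 1 as exploratory. It misses loss before Visit 2, the visit windows overlap (3-14 and 5-14 days), and there are only 10-15 subjects.

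A single split that fits the first hour and scores the second is not a good substitute: it compares a different part of the excursion with the full two hours at later visits, and a pessimistic Day 1 level could hide real drift.

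Cost: no extra fingersticks, visits or subjects, but the device company must re-run a proprietary program. With 24 fitted readings, each 30-minute block removes 6 and leaves 18, so the reference level is slightly pessimistic: √[(1 + p/18)/(1 + p/24)] = 1.01 for p = 2 and 1.05 for p = 10, on the same approximation as above. If only the first hour is fitted, the blocks come from 12 readings and this penalty is larger. The band is also removed after each visit, so left-out Visit 1 blocks share one placement. Any remaining difference reflects re-placement as well as drift and should be reported that way.
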